5.4.5 Additional Observations

Proportion of subjects that achieve therapeutic success. Therapeutic success is defined as freedom from AF, AFL (atrial flutter) and AT (atrial tachycardia, not including sinus tachycardia) following the blanking interval through Month 12. Proportion of subjects that achieve therapeutic success. Therapeutic success is defined as freedom from AF, AFL (atrial flutter) and AT (atrial tachycardia, not including sinus tachycardia) following the blanking interval through Month 12. For subjects to be considered a therapeutic success, they will have to be free of a confirmed AF, AFL or AT episode lasting 30 seconds or more after completion of the blanking interval. If a qualifying episode of AF, AFL or AT is found during the 24-hour continuous ECG monitor at Months 6 or 12, during any scheduled or unscheduled 12-lead ECG, or during the use of an event monitor after the blanking interval, the subject will be considered a therapeutic failure. In addition, subjects will be considered a therapeutic failure if they have a repeat ablation procedure at any time through Month 12 or if they received DC cardioversion or Vaughan-Williams Class I or III antiarrhythmic drug therapy for the treatment or prevention of AF, AFL or AT after the end of the blanking interval through Month 12. However, subjects will not be considered therapeutic failures if they received DC cardioversion or Vaughan-Williams Class I or III antiarrhythmic drug therapy for treatment of non-AF arrhythmias during the blanking period. Finally, any subject death after the blanking interval and prior to the Month 12 visit will be adjudicated by the CEC. In the absence of evidence regarding the presence or recurrence of AF following the blanking period, these subjects will be considered lost to follow-up. If, on the other hand, there has been evidence of the presence or

recurrence of AF following the blanking period, these subjects will be considered therapeutic failures.

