7.4 Imputation for Missing Data

Imputations for missing data in (e.g., withdrawn subjects, loss to follow-up, missing data) will not be performed. Analyses will be performed with all available data only.

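### In 5.4.5 the rule for deaths after blanking tests only for AF, while therapeutic failure is defined more widely, and the plan does not say which rule prevails

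*Combined protocol and SAP*

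**What the plan says.** Therapeutic success is an additional observation in 5.4.5, neither a primary nor a secondary endpoint. The section sets out three routes to failure:

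- Arrhythmia: a confirmed episode of 30 seconds or more after blanking, for example "If a qualifying episode of AF, AFL or AT is found during the 24-hour continuous ECG monitor at Months 6 or 12".
- Repeat ablation: "subjects will be considered a therapeutic failure if they have a repeat ablation procedure at any time through Month 12".
- Treatment after blanking through Month 12: "if they received DC cardioversion or Vaughan-Williams Class I or III antiarrhythmic drug therapy for the treatment or prevention of AF, AFL or AT".

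The section then turns to deaths: "any subject death after the blanking interval and prior to the Month 12 visit will be adjudicated by the CEC". Two branches follow. In the first, "In the absence of evidence regarding the presence or recurrence of AF following the blanking period, these subjects will be considered lost to follow-up". In the second, where there has been evidence of the presence or "recurrence of AF following the blanking period, these subjects will be considered therapeutic failures".

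Section 7.4 rules out imputation, naming loss to follow-up among the cases, and adds: "Analyses will be performed with all available data only". Section 5.11 ties lost-to-follow-up status to at least three unanswered contact attempts within 60 days. Section 7.1 describes a descriptive study without hypothesis tests, whose results will feed the design of later studies. Section 5.5 sets enrolment at up to 25.

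**The concern.** One endpoint carries two tests of failure. AFL, AT, repeat ablation, cardioversion and antiarrhythmic drug therapy all count in the general definition, but neither death branch names any of them. Take two subjects with the same flutter episode on the Month 6 monitor and no AF. The one alive at Month 12 is a failure. The one who dies on day 300 has no evidence of AF, and so falls literally into the lost-to-follow-up branch.

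If that subject then drops out of the analysis, the success proportion rises because a subject who met a failure criterion has died. The opposite mismatch exists too: the death rule asks for neither confirmation nor a 30-second duration.

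Failure without AF is foreseeable here. Section 3.1 says that gaps in lesion sets can create a substrate for reentrant atrial tachycardia. Section 5.13.5 allows gaps to be closed at the 3-month remapping at the investigator's discretion, without requiring an AF recurrence.

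**Working it through.** The plan gives no expected success rate, alpha, power or effect size, so there is no figure to reproduce. The check compares the two rules and then illustrates the size.

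**1. The rules side by side (5.4.5)**

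| What happened after blanking | Alive at Month 12 | Died before Month 12, death rule read literally |
|---|---|---|
| Confirmed AF, 30 s or more | failure | failure |
| Confirmed AFL or AT, 30 s or more, no AF | failure | lost to follow-up |
| Cardioversion or Class I/III drug for recurrent AF | failure | failure (the treatment is itself evidence of AF) |
| The same treatment for AFL or AT, or a preventive drug, no AF | failure | lost to follow-up |
| Repeat ablation for recurrent AF | failure | failure |
| Repeat ablation without AF | failure | lost to follow-up |
| Only a short or unconfirmed AF run | not a failure on that event | failure |

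The rules disagree in four of the seven rows: three move a failure out, and one creates a failure. Repeat ablation during blanking is not in the table, because 5.13.5 already makes it a failure with exit from the study.

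**2. Does a narrower reading remove the conflict?** Suppose that the death rule covers only subjects who have not already failed. Its second branch is then almost redundant, because qualifying AF after blanking is a failure anyway. What remains is mainly AF that does not qualify, which is the last row. Each reading therefore leaves a mismatch.

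**3. Size per affected subject.** Assume n = 25 evaluable subjects, s successes, and k deaths that met a failure criterion without AF. Kept as failures, the proportion is s/n. Left out, it is s/(n − k).

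| s (assumed) | kept, s/25 | k = 1, s/24 | shift | k = 2, s/23 | shift |
|---|---|---|---|---|---|
| 15 | 60.0% | 62.5% | +2.5 | 65.2% | +5.2 |
| 18 | 72.0% | 75.0% | +3.0 | 78.3% | +6.3 |
| 20 | 80.0% | 83.3% | +3.3 | 87.0% | +7.0 |
| 22 | 88.0% | 91.7% | +3.7 | 95.7% | +7.7 |

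For comparison, the exact (Clopper-Pearson) 95% interval for 18/25 is 50.6% to 87.9%, about 37 points wide.

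**4. How likely is it?** The documents give no rates. Assume that a proportion d = 1% to 4% of subjects die between Month 3 and Month 12, and that a proportion q = 10% to 30% of those deaths follow a failure without AF.

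- Expected number affected: 25 × d × q, from 25 × 0.01 × 0.10 = 0.025 to 25 × 0.04 × 0.30 = 0.3.
- Chance of at least one: 1 − (1 − dq)^25, from 1 − 0.999^25 = 2.5% to 1 − 0.988^25 = 26%.

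**5. The other direction.** A subject who dies with only a short AF run is now a failure, giving s/25. With the criteria aligned that subject is no longer a failure. If deaths without prior failure are left out, the proportion becomes s/24, the same rise of 2.5 to 3.7 points. If they stay in the denominator as non-successes, it remains s/25.

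**The case against.** A reader might infer that death erases an established failure. The documents do not say so. The failure sentences are unconditional, and nothing in the death rule says that it overrides them. It can be read as dealing only with subjects who had not yet failed. That stands: reclassification is one reading, and what can be shown is a conflict without stated precedence. The narrow reading has its own weakness, because the rule opens with any death, has no exception for prior failure, and is left with a nearly empty second branch.

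AF may also be shorthand for all three arrhythmias. Section 5.13.5 provides the event monitor to capture AF, yet 5.4.5 scores AF, AFL or AT found on it. This weakens the literal reading but does not settle it. Section 5.4.5 otherwise lists the three separately, and just before the death rule it treats arrhythmias other than AF as a class of their own.

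It would also be too strong to say that every treatment route escapes the death rule. Cardioversion, drug therapy or repeat ablation given for recurrent AF would ordinarily be evidence of AF, and the subject would fail under either rule.

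Nor does 7.4 expressly drop the subject. It bars imputation and uses available data, and a recorded flutter episode is available data. No section sets the denominator for subjects lost to follow-up, so leaving the denominator is probable rather than written.

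Finally, the expected number affected is well below one under the assumed rates. That stands, and it limits the severity.

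**Conclusion.** The point holds in a limited form. Section 5.4.5 applies a narrower test to deaths than to living subjects and states no precedence. The gap covers failures without evidence of AF: AFL or AT, treatment for AFL or AT, preventive drug use, and repeat ablation without AF. Such a subject who dies may be classed as lost to follow-up, a label that does not fit 5.11 either.

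If the subject also leaves the denominator, the success proportion rises by about 2.5 to 3.7 points each. This rests on 25 evaluable subjects, 15 to 22 successes, and an assumed number affected that may be zero. The shift is small beside the sampling uncertainty.

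The documents do not support the stronger inference that the plan necessarily converts failures into losses, or that the present wording can err only in favour of success. The severity is minor: this is a descriptive additional observation with no hypothesis test. It is still worth settling before outcomes are known, because it is a written rule that can misclassify, and 7.1 intends the results to inform later studies.

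**What to change.** In 5.4.5:

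1. State that any therapeutic failure criterion met before death stands.
2. In both death branches, replace the test for AF with a test for any therapeutic failure criterion defined earlier in the section. This brings in AFL, AT, repeat ablation and treatment, and it applies the confirmation and 30-second conditions to deaths as well.
3. Report deaths without prior failure as deaths, and keep lost to follow-up for the situation in 5.11.
4. State the denominator for those deaths. If the main figure leaves them out, add a sensitivity figure that counts them as failures.

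Possible wording: *A subject who dies after the blanking interval and before the Month 12 visit is a therapeutic failure if any criterion above was met before death. Otherwise the subject is reported as a death without prior failure, and is [included in / excluded from] the denominator.*

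The cost is a few sentences and no new data. The success figure will usually become slightly less favourable, but it could rise if a subject who died had only a non-qualifying AF run.

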5.5 Sample Size

Up to 25 subjects will be enrolled in this clinical trial.

5.6 Investigational Sites

The clinical trial will be conducted at up to 3 clinical sites in Europe.

5.7 Duration of Subject Participation

Subjects enrolled in the trial will participate for approximately 18 months. This includes the baseline evaluation, the procedure and follow-up evaluations at 1 month, 3 months, 6 months, 9 months and 12 months post-procedure.

5.8 Written Informed Consent

All subjects must provide written Informed Consent using the Ethics Committee approved Informed Consent Form before undergoing any study related procedures. Subjects cannot be asked to sign the Informed Consent document until the trial has been fully approved by the respective institution's EC and the Sponsor or their CRO representative has received and reviewed the specific EC-approved Informed Consent Form. Subjects who meet the general entry criteria will be asked to sign a Patient Informed Consent form as approved by the relevant regulatory authorities before any study-specific tests or procedures are performed. The Investigator or a designated member of his/ her staff should approach the subject to obtain written informed consent. As far as possible, non-technical language shall be used that is understandable to the subject. If the family of the subject is available, they should also be consulted. The background of the proposed study and the benefits and risks of the procedures and study should be explained. The subject should be provided with ample time to read the consent form and discuss it with their family and physician. The subject shall be informed that his/ her participation in the clinical investigation is confidential. The Informed Consent Form must be read and understood by the subject and the subject's questions answered. The form must be signed and dated by both the subject and investigator conducting informed consent before the subject undergoes any study related procedures. All subjects are to receive copies of their signed and dated Informed Consent Form. A copy of the approved informed consent form along with a copy of each patient's signed consent form will be maintained by each Investigator in a designated clinical study administrative file. The subject and the investigator must sign the consent form prior to enrollment. Subjects may not be consented after receiving any medication that might alter their ability to comprehend the consent form (e.g. sedatives, narcotics, etc.). Study personnel should explain that even if a subject agrees to participate in the study and signs the Patient Informed Consent form, the subject may not be eligible to participate if he/ she fails to meet the screening criteria.

Written informed consent must be obtained prior to performing any protocol driven tests or any procedures that are not standard of care for a cardiac surgery that the subject is scheduled to undergo.

Once written consent has been obtained, the subject will be entered on a Screening Log, which will be maintained at each site. All subjects who provide written informed consent will be entered on the screening log regardless of whether or not they are enrolled in the study.

5.9 Enrollment

Subjects that meet all the eligibility criteria and are deemed suitable by the investigator will be invited to participate in the study.

Subjects will be considered enrolled at the time of signing the informed consent.

Each subject will be assigned a unique study identification code to protect each subject's confidential health information. The unique study identity code will not include date of birth or subject's first and last initials and will be used to link study data and other study information to the subject in lieu of the subject name. The Subject Name Log will be used to link the unique study identity code to the subject and will be maintained at each site. This log will remain confidential and will not be provided to the Sponsor, but only used for reference when monitoring at the study site.

5.10 Withdrawal of Subjects

Subjects may voluntarily withdraw from the trial at any time for any reason. In addition, the investigator may withdraw the subject due to any of the following situations:

- adverse event (AE); or
- any other reason determined by the investigator to be in the best interest of the subject.

Subjects with an ongoing AE at the time of withdrawal should be followed on study until the clinical event has been resolved or is stable if at all possible.

5.11 Lost to Follow-up

If the investigator has attempted to contact a subject at least three times within 60 days and received no response, the subject may be considered lost to follow-up. The investigator will document that a minimum of three attempts were made to contact the subject, including sending a certified letter if current address is known, prior to exiting the subject from the trial.

5.12 Subject Confidentiality

All information concerning subjects or their participation in this trial will be considered confidential. Only authorized Sponsor and designated representative personnel and designated consultants and regulatory agencies will have access to these confidential files. Enrolled subjects will be assigned

a unique, anonymous identifier that will be used to maintain confidentiality of each subject's medical information. Subject names and other protected health information will not be captured on the case report forms. In addition, all patient identifiers except the unique anonymous identifier should be redacted from any x-ray and MRI images submitted from the participating site to the Sponsor or the Sponsor's designated reviewers for analysis.

5.13 Schedule of Events and Assessments

Subjects will complete the following visits and assessments as indicated below and in Table 4.

5.13.1 Baseline

The following baseline data will be collected:

- Medical history
- Medication history
- Pregnancy test (if applicable)
- 12-lead ECG
- Cardiac CT or MRI
- NYHA Classification
- TEE or other imaging modality for exclusion of left atrial thrombus

5.13.2 Procedure

For a detailed description of procedure workflow refer to LBL0026 and LBL0027. Procedural details will be captured in study CRF. The following procedural data will be collected:

- Medications administered
- Pre- and post-ablation electro-anatomical maps
- Anticoagulation monitoring (e.g. ACT)
- Adverse event(s)

5.13.3 Pre-Discharge

Prior to hospital discharge the following data will be collected:

- Use, changes in or discontinuation of anticoagulation, rate control and/or antiarrhythmic medications;
- Cardioversion(s) since surgery;
- For subjects on warfarin, assessment of INR therapeutic levels (maintain as clinically indicated);
- For subjects on dabigatran, perform a PTT and, if required, a thrombin time (Section 4.7.2.7 Anticoagulation Regimen);

- Cardiac rhythm as determined by a 12-lead ECG on day of hospital discharge;
- Heart failure status as assessed by NYHA classification on day of hospital discharge; and Adverse Events.

5.13.4 1 Month Follow-Up

Discharged subjects will return for an office visit 30 days (± 7 days) postablation treatment. Subjects that continue to be hospitalized 30 days postablation will have their 30-Day Follow-Up assessment performed at discharge. At a minimum, the following data will be collected at 30 Day Follow-Up visit:

- Use, changes in or discontinuation of anticoagulation, rate control and/or antiarrhythmic medications;
- Cardioversions since last visit;
- For subjects on anticoagulants, assessment of INR/PTT therapeutic levels (maintain as clinically indicated):
- Cardiac rhythm as determined by a 12-lead ECG at the time of the visit;
- Heart failure status as assessed by NYHA classification at the time of visit;
- Any hospital readmissions, including admission and discharge dates, since discharge from the original procedure; and

5.13.5 3 Month Follow-Up

Subjects will return for an office visit at the end of the blanking period (90 days \pm 14 days post-ablation treatment). During the blanking period, any recurrence of AF will be documented; however, recurrences of AF, AFL or AT during this time will not be considered therapeutic treatment failures. Subjects are not permitted to undergo repeat ablation during the blanking period. If a repeat ablation procedure is performed during this time, the subjects will be considered a therapeutic treatment failure and exited from the study.

At a minimum, the following data will be collected at the end of the blanking period follow-up visit:

- Use, changes in or discontinuation of anticoagulation, rate control and/or antiarrhythmic medications;
- Cardioversions since last visit;
- Any additional ablation procedures performed;
- For subjects on anticoagulants, assessment of INR/PTT therapeutic levels (maintain as clinically indicated);

- Cardiac rhythm as determined by a 12-lead ECG at the time of the visit;
- Heart failure status as assessed by NYHA classification at the time of visit;
- Any hospital readmissions, including admission and discharge dates, since the previous visit; and
- Adverse events.
- If a subject is symptomatic for AF at the end of the blanking period, an event monitor will be provided to be used up to the 6-month follow-up visit to capture AF episodes.
- Patients will undergo an electro-anatomical remapping procedure to assess electrical isolation of the posterior left atrium and pulmonary veins. Any electrical gaps may be closed at the investigator's discretion using a commercially approved ablation device. This will consist of placement of catheters in the left atrium via femoral access and transeptal puncture using conventional electrophysiology techniques.
- Patients will undergo a cardiac CT or MRI scan at 3 months to assess the patency of the pulmonary veins.

5.13.6 6 Month Follow-up

Subjects will return for an office visit 6 months (180 days \pm 30 days) postablation treatment. At a minimum, the following data will be collected at 6 months:

- Use, changes in or discontinuation of anticoagulation, rate control and/or antiarrhythmic medications;
- Cardioversions since last visit;
- · Any additional ablation procedures performed;
- For subjects on anticoagulants, assessment of INR/PTT therapeutic levels (maintain as clinically indicated);
- Cardiac rhythm as determined by a 12-lead ECG at the time of the visit;
- Heart failure status as assessed by NYHA classification at the time of visit;
- Cardiac rhythm as determined by a 24-hour continuous ECG monitor following the visit for subjects in NSR at the time of the visit;
- Any hospital readmissions, including admission and discharge dates, since the previous visit; and
- Adverse events.

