5.4.2 Secondary Safety Endpoint

The proportion of subjects reporting one or more SAEs for each follow-up interval. The intervals will include the period from:

- The surgical procedure for the surgical PEF ablation through the Day 30 follow-up visit;
- The Day 30 follow-up visit through the Month 3 follow-up visit;

- The Month 3 follow-up visit through the Month 6 follow-up visit; and
- The Month 6 follow-up visit through the Month 12 follow-up visit.

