7.1 General Statistical Considerations

The primary objective of this study is to characterize the safety and feasibility of the FARAPULSE Cardiac Ablation System in subjects with paroxysmal atrial fibrillation undergoing cardiac surgery.

The study is a feasibility study with no formal hypothesis testing and therefore no required sample size. Study results will be presented using descriptive statistics. Results from this study will be used to design additional clinical studies.

All subjects will be followed on an intent-to-treat basis. The device performance will be assessed based on a per-protocol analysis of the primary safety and feasibility endpoints and secondary efficacy endpoints. An intent-to-treat analysis, along with other secondary analyses, will also be completed and reported.

Demographic, baseline clinical and disease characteristics, procedural results and primary, secondary and all additional endpoints will be summarized using descriptive statistics.

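### Section 5.13.5 exits subjects re-ablated during blanking, which conflicts with intent-to-treat follow-up in 7.1 and ends new-SAE collection for a group selected by outcome

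*Combined protocol and SAP*

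**What the plan says.** Section 5.13.5 does not permit repeat ablation during the 3-month blanking period and sets the consequence: "If a repeat ablation procedure is performed during this time, the subjects will be considered a therapeutic treatment failure and exited from the study".

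Four other parts of the plan bear on this:

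- **Follow-up principle (7.1).** "All subjects will be followed on an intent-to-treat basis". The section bases device performance on a per-protocol analysis and also promises an intent-to-treat analysis.
- **Scoring (5.4.5).** "subjects will be considered a therapeutic failure if they have a repeat ablation procedure at any time through Month 12". This covers the blanking period and does not mention exit.
- **Secondary safety endpoint (5.4.2).** "The proportion of subjects reporting one or more SAEs for each follow-up interval", over four intervals that run from surgery to the Month 12 visit. It counts any SAE, whether or not it is related to the device.
- **Missing data (7.4).** Nothing is imputed: "Analyses will be performed with all available data only".

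At the Month 3 visit, 5.13.5 also schedules imaging: "Patients will undergo a cardiac CT or MRI scan at 3 months to assess the patency of the pulmonary veins". Table 4 lists no other cardiac CT or MRI after the procedure.

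**The concern.** A subject re-ablated within three months is likely to be one whose lesion failed or whose arrhythmia came back. The exit rule removes exactly these subjects from further observation. In a first-in-man study of up to 25 people, whose stated use is to design later studies, late safety in such subjects is part of what has to be learned.

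The rule also treats like cases differently. A re-ablation on day 120 is a therapeutic failure who stays in follow-up. One on day 60 is a therapeutic failure who leaves. The plan gives no reason for the difference.

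What is at stake is the late SAE proportions and, for an exit before the Month 3 visit, the check for pulmonary vein narrowing. Severe pulmonary vein stenosis is a named component of the primary safety composite in 5.4.1.

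**Working it through.** The plan gives no figure for this point: there is no hypothesis test, and the sample size is not derived. The check is therefore a comparison of texts, followed by illustrative arithmetic.

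**1. Does safety collection stop at exit?** Section 8.2 monitors AEs and SAEs from enrollment until discharge from the trial. Section 5.10 keeps a withdrawn subject under follow-up for AEs already ongoing, and 8.2 follows reported AEs until resolved or stable. Section 5.15 describes ordinary exit as following the final visit. No section provides for new events after an early exit. This is an inference from silence, but no text points the other way. The wording on discharge in 8.2 is loose; if it meant hospital discharge, collection under 8.2 would end sooner still.

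**2. What does one exit lose?** Days lost = 365 − exit day. The follow-up visits are Day 30, Month 3, Month 6 and Month 12.

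| Exit | Days lost | Visits lost | SAE intervals lost whole |
|---|---|---|---|
| Day 30, at that visit | 365 − 30 = 335 (91.8%) | 3 of 4 | 3 of 4 |
| Day 60 | 365 − 60 = 305 (83.6%) | 3 of 4 | 2 of 4, plus the rest of Day 30–Month 3 |

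Both exits also lose the Month 3 CT/MRI. The Month 3 remap is lost too, but a remap after a second ablation would say little about the study device.

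**3. What does one exit do to an interval SAE proportion?** Assume 25 treated, one exit, and x subjects with an SAE among the other 24. Under 7.4 the report is x/24. The full-follow-up value is (x + 1)/25 if the exited subject has a later SAE in that interval, and x/25 if not.

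| x | Reported x/24 | Full, later SAE | Full, no later SAE | Error (points) |
|---|---|---|---|---|
| 1 | 4.2% | 2/25 = 8.0% | 1/25 = 4.0% | −3.8 or +0.2 |
| 3 | 12.5% | 4/25 = 16.0% | 3/25 = 12.0% | −3.5 or +0.5 |
| 5 | 20.8% | 6/25 = 24.0% | 5/25 = 20.0% | −3.2 or +0.8 |

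**4. More than one exit.** With k exits and no late SAE observed, the proportion among all 25 could be as high as k/25: 4% for k = 1, 8% for 2, 12% for 3 and 20% for 5. The exact two-sided 95% upper limit barely reflects this. It is 13.7% for 0/25, 14.2% for 0/24 and 16.8% for 0/20, because it treats the missing subjects as if they were like the rest.

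**5. What is not affected?** Procedural success is settled at the index operation. Therapeutic success is settled by 5.4.5, since the subject is already a failure. A known phrenic palsy would still be followed under 5.10 and 8.2, so the 12-month phrenic component of the primary composite is exposed mainly to undetected cases or cases not followed to Month 12.

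**The case against.** The strongest defence is that exit is deliberate and rarely used. Repeat ablation in blanking is prohibited, so the rule applies only after a deviation. Section 6.1.1 says that further ablation after recurrence may be pursued outside the study. Section 7.1 bases device performance on the per-protocol analysis, where a re-ablated subject may have little place. The trial is descriptive, one exit moves the zero-event upper limit only from 13.7% to 14.2%, and the error is below one point unless the exited subject has a later SAE.

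Much of this stands as a limit on size. It does not remove the conflict. Placing a second ablation outside the study does not say that safety observation ends, and a per-protocol performance analysis does not require exit. The small change in the upper limit measures lost precision and leaves out the selection.

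Two stronger readings are tempting, and the documents do not support them.

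- **That exit contradicts the death rule in 5.4.5.** That section says "any subject death after the blanking interval and prior to the Month 12 visit will be adjudicated by the CEC". The sentence serves the classification of therapeutic success: such deaths are scored as lost to follow-up or as failures. A subject re-ablated in blanking is already a failure, so nothing there is contradicted.
- **That gap closure at the Month 3 remap triggers exit.** Section 5.13.5 allows it: "Any electrical gaps may be closed at the investigator's discretion using a commercially approved ablation device". The visit window of 90 ± 14 days covers days 76 to 104, which is 29 days, 14 of them before day 90. For a closure on those days to trigger exit, closure must count as repeat ablation and blanking must end on a fixed day whenever the visit takes place. The plan states neither. Section 5.13.5 and Table 4 place the visit at the end of blanking, and the same section expressly permits the closure. This is a matter for clarification only.

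A further objection is fair and shapes the fix. The secondary safety endpoint has no relatedness filter, so retained subjects may add SAEs caused by a second, commercial device.

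**Conclusion.** The point holds and should be fixed. The exit rule in 5.13.5 conflicts with 7.1, is not needed for any endpoint, and removes a group selected by outcome from at least two of the four SAE intervals. It removes them from three if exit comes at about the Day 30 visit. An exit before the Month 3 visit also loses the only scheduled post-procedure pulmonary vein scan.

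The size is uncertain. The documents give no expected number of early re-ablations, and it may be zero. Per exit, with 25 treated and 1 to 5 SAE subjects among the other 24, an interval proportion is reported 3.2 to 3.8 points too low if the exited subject has a later SAE, and 0.2 to 0.8 points too high if not. This rests on three assumptions: all 25 places are filled and treated, exited subjects leave the denominator under 7.4, and new SAEs are not collected after exit.

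The documents do not support a claim that the procedural or therapeutic success results are distorted, or that permitted gap closure leads to exit.

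**What to change.** In 5.13.5, keep the therapeutic-failure scoring and replace the exit instruction with safety follow-up through Month 12. In 5.4.2 and 7.7.2, state that interval SAE proportions are reported for all treated subjects, with SAEs occurring after a repeat ablation also shown separately.

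As a clarification, add to 5.13.5 that gap closure at the scheduled Month 3 remap does not breach the blanking-period ban and is recorded separately from other repeat ablation. Whether such closure counts as therapeutic failure is an endpoint definition that the plan leaves open, and this change should not settle it.

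The cost is a few sentences, a CRF field, and one added line in the SAE tables. The visits are already in Table 4, so the extra burden is the remaining scheduled visits, and the Month 3 CT/MRI after an earlier re-ablation, for perhaps a few subjects. The downside is that some later SAEs may come from the second ablation. The separate display and the relatedness adjudication already planned in 7.7.1 make that visible.
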